Shortly after diagnosis of T1DM, many children and adolescents not uncommonly experience a honeymoon period [10]. It occurs because there is a sufficient amount of residual B-cell mass that enables some of these individuals to secrete some endogenous insulin. As a result, in order to prevent hypoglycemia, these individuals may be managed with less exogenous insulin over a short period of time [11]. This variability makes less accurate HbA1C concentration as a gold standard for assessing glucose control in the first 6-12 months after diagnosis [12,13].

Glycemic variability (GV) obtained from multiple blood glucose levels (up to 6 – 10 times/day) provides a good correlation for an individual's glycemic control and predictor of chronic diabetic complications [3]. The GV refers to swings in blood glucose levels and captures blood glucose oscillations that occur throughout the day, including hypoglycemic periods, postprandial increases, as well as blood glucose fluctuations that occur at the same time on different days [14]. The proposed target range of 70–180 mg/ dl is considered acceptable for clinical practice, as it has been observed that if 50% of the self-monitoring of blood glucose readings are in this range, the A1C would be ~7% [12,13]. Shapiro et al, reported that teens and parents show some similarities in the facets comprising distress, including negative emotions about diabetes and the demanding diabetes regimen [15]. Simplified insulin treatments will remarkably help to maintain adherence and to prevent deterioration in glycemic control.

For the purposes of this study the following definitions will be used:

BMI: Weight (kg)/ Height (m²).

Glycemic variability: Blood glucose oscillations that occur throughout the day. The glycemic range on target is between 80 – 180 mg/dl.

Insulin dose adjustment: Titration of insulin over time to improve glycemic control.

Parental stress: Stress associated to caring for a child with diabetes.

Insulin to carbohydrate ratio (ICR): Number of carbohydrates that 1 unit of rapid-acting insulin covers.

Basal insulin: Insulin that controls blood sugar consistently for 24 hours.

Rapid-acting insulin: Mealtime insulin. Typically has onset in 10 - 15 minutes, peaks at 45 – 60

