5. APPROACH –RESEARCH METHODS

A. STUDY DESIGN

Two - Arm, Randomized, Clinical trial (See Figure 1)

This proposal is designed to compare children and adolescents with newly diagnosed T1DM using a fixed insulin dose for fixed carbohydrate mealtime regimen (FIXED group) to children and adolescents with newly diagnosed T1DM using an ICR with variable carbohydrate intake (ICR group) mealtime regimen and determine:

1) Specific Aim 1

Determine the feasibility for a subsequent clinical trial involving rapid acting insulin dosing for a fixed dose for fixed carbohydrates (FIXED group) vs ICR with variable carbohydrate intake (ICR group) in order to determine the capacity for recruitment, caregiver consent to random assignment and completion of study measures, average session attendance, caregiver treatment adherence, and post-treatment satisfaction.

2) Specific Aims 2

- a) Determine if the caregivers of diabetics using a fixed insulin for fixed carbohydrate regimen (FIXED group) experience less anxiety than the caregivers of those using an ICR with variable carbohydrate intake regimen (ICR group) at 1- and 4-months post-randomization.
- b) Determine if diabetics utilizing a fixed insulin for fixed carbohydrate regimen (FIXED group) have decreased glycemic variability (GV) than those using an ICR with variable carbohydrate intake regimen (ICR group) at 1- and 4-months post-randomization.

We hypothesize that we will recruit and consent enough patients in order to perform a future, larger trial where caregivers of children and adolescents with newly diagnosed T1DM using a fixed insulin for fixed carbohydrate mealtime regimen (FIXED group) will experience less anxiety and their diabetic children will experience less GV than children and adolescents with newly diagnosed T1DM who use an ICR with variable carbohydrate intake at mealtime (ICR group). If this proves to be true, less anxiety may encourage more compliance and better glycemic control.

[figure not shown]

Figure 1: Study design and hypothesis.

3) Methods

a) Recruitment & Consent

Subjects with newly diagnosed T1DM will be evaluated by authorized study personnel under a HIPAA waiver to determine potential eligibility. The subjects will be contacted by the research study team while in the hospital during his or her initial diagnosis to explore his/her interest in the study and to confirm eligibility. The informed consent/assent documents will be signed at the time of the initial contact.

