The primary goal of this study is to determine the feasibility of a subsequent clinical trial of rapid acting insulin dosing for fixed carbohydrates (FIXED group) vs ICR with variable carbohydrate intake (ICR group). In doing so, we will examine our ability to recruit and consent patients (>70% consent rate), study retention (>90% retention), completion of study visits (average session attendance \geq 90%), study measures (\geq 90% measure completion), caregiver treatment adherence, and post-treatment satisfaction (\geq 90%),

2) Secondary Outcomes Measures

Secondary outcome measures will include caregiver anxiety and glycemic variability. Each of these measures are described below.

One secondary outcome measure is caregiver anxiety. This will be assessed by a parental stress scale [17]. The caregiver will fill out the questionnaire at initial enrollment (prior to hospital discharge) and at each clinic follow-up throughout the study. We will use the Spanish adaptation of parental stress scale (PSS) [18] for Spanish population if necessary.

We clarify in the survey that the questions are to be answered in terms of how the caregiver-child relationship exists since the diagnosis of diabetes mellitus.

The scales are shown in **Annex 1 and 2**

Glycemic variability (GV) is another secondary outcome measure. The GV will be calculated in all subjects through the use of a glucose monitor (GM) data classification scale. Subjects will be considered to have appropriate GV if their blood glucose level is in the range of 80 mg/dL – 180 mg/dL (Group C).

The GV classification is as follows:

Group A: < 50 mg/dl.

Group B: 50 – 79 mg/dl

Group C: 80 – 180 mg/dl

Group D: 181 – 350 mg/dl

Group E: > 350 mg/dl

Safety is the last secondary outcome measure. The safety measured that will be compared in both groups include death, risk of life threatening event (i.e., severe hypoglycemia associated with seizure or altered mental status), hospitalization for diabetes complication (diabetic ketoacidosis or hypoglycemia), and risk of disability or permanent damage.

E. STATISTICAL CONSIDERATIONS

Randomization

Randomization will be performed by study statistician using random-permuted blocks of size 2 and 4. Randomization assignments will be placed in sealed, opaque envelopes to be stored. Study investigators will not be blinded to treatment assignment.

Sample Size

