A goal of 20 patients is necessary for this study, but we will reach up to 40 participants in case there is any withdraw after consented and randomized. While the overall goal of the study is to demonstrate feasibility of a subsequent randomized controlled trial, limited efficacy testing will be performed. Given a sample size of 20 participants (10/grp), we will have greater than 90% power to detect a minimum standardized mean difference of 1.25 (i.e., approximately a 1.25 standard deviation difference) between groups. Effect sizes will be calculated for all study measures of interest and be used in future power calculations. On average, there are ~25 new type I/II diabetics diagnosed at Egleston hospital each month. Assuming an eligibility rate of 40%, 10 patients would be eligible to participate each month. Based on this, we are confident in our capacity to recruit 20 to 40 participants during the study period with the goal of having 20 participants to complete the study.

Statistical Analysis

Demographic characteristics will be summarized for both groups using means and standard deviations, medians and quartiles, or counts and percentages, as appropriate based on distribution. T-tests, Wilcoxon rank sums, and/or Chi squared tests will be used to assess differences between the two groups.

Primary Aims: Measures of feasibility (consent, retention, engagement, satisfaction, etc.), will be summarized overall and by group, when applicable.

Secondary Aim 1: Parental stress scale

The parental stress scale will be scored per the instrument's instructions. The total scores for the treatment groups will be compared in a cross-sectional fashion using t-tests or Wilcoxon rank sums tests as appropriate based on the distribution of scores. Changes in parental distress over-time will be evaluated using two-way repeated measures analysis of variance models. Models will include the main effect of treatment assignment, time (baseline, 1 month, 4 months), and the treatment X time interaction. The interaction term will serve as the primary statistical test for aim 2. Summary statistics, statistical significance, and effect sizes will be reported by group at each time point of interest, when applicable.

Secondary Aim 2: Glycemic variability

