Glycemic variability will be examined both as a continuous variable and a categorical variable using the ranges defined in section D. Time series analysis will be used to examine daily measures of blood glucose (obtained from patient diary's) during the study period. Variability will be measured as the probability of acute change (PAC), using methods described by Jahnig et al. (2008). Acute changes will be adjusted for time between readings. In addition, first-order autocorrelations and/or mean-square successive difference will be used to examine variation in readings as described by Jahnig. Multilevel modeling will be used to test between-group differences in variability.

Secondary Aim 3: Safety

Adverse event of interest and serious adverse events (see section D) will be summarized overall and by treatment group. For participants experiencing more than 1 episode of a specific event (e.g., severe hypoglycemia), the maximum grade and severity will be recorded. Chi-square tests will be used to compare the frequency of events between the two cohorts.

Given the exploratory nature of these secondary outcomes, we will calculate effect sizes based on the adjusted means and standard deviations or differences in proportions, when appropriate.

All analyses will be conducted using SAS v9.4 (Cary, NC).

F. ANTICIPATED RESULTS

This research will be feasible to develop a successful larger clinical trial. Due to the fixed regimen seeming to be less complicated, because there are less calculations to make than in those using the ICR group, we anticipate that parental anxiety will be decreased in the FIXED group. This will encourage more blood glucose monitoring and treatment compliance. Therefore, we anticipate GV to be decreased for the FIXED group.

G. LIMITATIONS

The major limitations of this study are related to caregiver's self-completion questionnaire and ability to contact study personnel frequently during the study period in order to report blood glucose levels and implement the insulin adjustments. More than likely, multiple insulin regimens should work, but the idea behind this study is that the fixed regimen may be easier to implement.

[figure not shown]

Figure 2: Proposed protocol.

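### Glycemic variability is scored from bands of absolute glucose level, so a difference in mean glucose between arms can be reported as a variability effect for Aim 2b

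*Combined protocol and SAP*

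**What the plan says.** - **Definition (Section 4, study definitions).** "Glycemic variability: Blood glucose oscillations that occur throughout the day". The same entry then gives an on-target glucose range of 80–180 mg/dL.
- **Aim (Section 5.A, Specific Aim 2b).** The question is whether children in the FIXED group "have decreased glycemic variability (GV) than those using an ICR with variable carbohydrate intake regimen", at 1 and 4 months.
- **Outcome (Section 5.D.2).** "The GV will be calculated in all subjects through the use of a glucose monitor (GM) data classification scale". The scale has five bands: A below 50, B 50–79, C 80–180, D 181–350 and E above 350 mg/dL. "Subjects will be considered to have appropriate GV if their blood glucose level is in the range of 80 mg/dL" to 180 mg/dL.
- **Analysis (Section 5.E, Secondary Aim 2).** "Glycemic variability will be examined both as a continuous variable and a categorical variable using the ranges defined in section D". The paragraph then says that variability is measured by PAC, adjusted for the time between readings, and adds first-order autocorrelation and/or the mean-square successive difference (MSSD). It ends: "Multilevel modeling will be used to test between-group differences in variability".
- **Use of the results (Section 5.E, Sample Size).** "Effect sizes will be calculated for all study measures of interest and be used in future power calculations". The closing text on the secondary outcomes allows effect sizes as differences in proportions.

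**The concern.** A band of absolute glucose records where a reading lies, not how much readings move. A child steady at 230 mg/dL hardly oscillates, yet has no reading in the band that counts as appropriate GV. The share of readings in a band depends on both mean and spread, so under the GV label two errors are possible:

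- a difference in mean glucose alone is reported as a GV effect;
- a real fall in variability appears as worse GV, because the mean moved as well.

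Section 5.E does plan measures of oscillation, and its sentence order implies that PAC is what the multilevel model tests. That is only implied, and Section 5.D.2 says otherwise. The only test named as primary for aim 2 is the stress-scale interaction. If bands and PAC disagree, either could be reported as the GV result, and a band difference could enter the planning of the later trial as a variability effect. In addition, Section 5.D.2 classifies subjects, but no rule turns a child's many readings into one Group.

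**Working it through.** **Inputs.** The bands come from Section 5.D.2, and 10 per group from Section 5.E. The plan has no GV figure to reproduce, and gives no glucose mean, SD, autocorrelation or PAC cut-off. All such values below are assumptions chosen to show direction and rough size.

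**Formulas.**
- Group C share, normal readings: Φ((180 − mean)/SD) − Φ((80 − mean)/SD).
- For independent normal readings: MSSD = 2·SD², and P(|successive change| ≥ c) = 2[1 − Φ(c/(SD·√2))]. The PAC cut-off c = 80 mg/dL is assumed.

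**1. Mean differs, spread does not (SD 50).**
- Mean 150: Φ(0.6) − Φ(−1.4) = 0.7257 − 0.0808 = 64.5%.
- Mean 170: Φ(0.2) − Φ(−1.8) = 0.5793 − 0.0359 = 54.3%.
- MSSD is 2 × 50² = 5,000 in both arms, and the chance of a change of at least 80 mg/dL is 25.8% in both.

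Drop in the Group C share, in percentage points, for mean 150 to 170:

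| SD | Normal | Lognormal |
|---|---|---|
| 40 | 14.7 | 14.4 |
| 50 | 10.2 | 10.0 |
| 60 | 7.0 | 6.1 |
| 70 | 5.0 | 3.0 |

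**2. Variability falls, bands say worse (150/SD 50 versus 170/SD 40).**
- MSSD falls from 5,000 to 2 × 40² = 3,200.
- The chance of a change of at least 80 mg/dL falls from 25.8% to 15.7%.
- The Group C share for the second arm is Φ(0.25) − Φ(−2.25) = 0.5987 − 0.0122 = 58.6%, down from 64.5% (lognormal: 72.7% to 64.1%).
- With the same shifts (mean +20, SD −10), the share falls for every starting SD from 45 to 70 in steps of 5: by 0.8 to 8.0 points (normal) or 0.9 to 10.7 points (lognormal).

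**3. What a test would show.** Trials were simulated with 10 children per arm, 120 readings each, within-child SD 50, between-child SD 25, lag-1 correlation 0.3 and identical variability in both arms. Tests were two-sided t-tests at 0.05, with band edges at 79.5 and 180.5; there were 2,000 trials per row.

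| Mean difference (mg/dL) | Significant on Group C share | Significant on log MSSD |
|---|---|---|
| 0 | 4% | 4% |
| 20 | 29% | 5% |
| 30 | 60% | 5% |
| 40 | 84% | 5% |

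**4. No per-child rule.** A child with mean 178 and SD 60 (normal) has 46.2% of readings in C and 48.5% in D. The child is Group C by mean and Group D by most frequent band.

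**5. Limits of the planned measures.**
- If SD is proportional to the mean, SD at mean 170 is 50 × 170/150 = 56.7. MSSD is then 6,422, and 6,422/5,000 = 1.28. The chance of a change of at least 80 mg/dL rises from 25.8% to 31.8%. Absolute variability really has changed, but the mean is needed to interpret it.
- PAC depends heavily on its cut-off. At SD 50, c = 40, 80 and 120 mg/dL give 57.2%, 25.8% and 9.0%.
- Lag-1 autocorrelation is scale-free. In simulated series with the same innovations at SD 25 and SD 50 it is 0.398 in both, while MSSD is 750 and 2,999.

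**The case against.** The strongest reply is that Section 5.E already has the remedy. It measures variability by PAC, and its only between-group GV test refers to variability, so the bands can be read as a descriptive view. The Section 4 entry itself includes the 80–180 range, so Section 5.D.2 follows a mixed definition rather than departing from a pure one. A result given with its cut-points is visibly about level. The numerical cases are constructed: the child in step 4 sits 2 mg/dL below a band edge, and in step 2 the effect shrinks to under 1 point at a starting SD of 70. The outcome is exploratory, in a feasibility pilot.

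Much of this stands. PAC is the natural reading, the sizes are illustrations, and the stakes are modest. The missing PAC cut-off, the missing per-child rule and the ranking of MSSD and autocorrelation are specification points that would not carry the concern alone.

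It does not remove the conflict. The range in Section 4 is a glucose target, not a measure of oscillation. Section 5.D.2 says that GV is calculated from the bands, and Section 5.E keeps them as a GV analysis beside PAC, with no stated order between the two.

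**Conclusion.** The concern holds. As written, the plan lets a level outcome be reported as glycemic variability, and it can give the wrong sign for Aim 2b. For a 20 mg/dL difference in mean with unchanged spread, the Group C share falls by about 3 to 15 points over SD 40–70, normal or lognormal. These sizes rest wholly on assumed glucose distributions. That band shares respond to the mean does not depend on the particular values chosen.

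The effect is on interpretation of an exploratory secondary outcome and on planning of the later trial, where use of a band effect as a GV effect is possible rather than certain. Band shares remain informative about glycemic control. The change should be made, but it is a correction of wording and labelling.

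**What to change.** In Sections 5.D.2 and 5.E (and by reference in the Section 4 definition):

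1. Relabel Groups A–E as a glucose-level (glucose-in-range) outcome. Summarise it as each child's percentage of readings per band at 1 and 4 months, which also removes the need to assign a child to one Group. State that it is not evidence on variability.
2. State that the Aim 2b test and its effect size rest on PAC, as Section 5.E already implies, with MSSD supportive and lag-1 autocorrelation descriptive only, since it cannot by itself show reduced amplitude. Before data are seen, state the size of change that counts as acute. Section 5.E gives none, and the 2008 method paper it relies on is missing from the reference list in Section 16.
3. Report mean glucose by arm beside PAC and MSSD, because both can move with the mean if spread scales with level.

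The cost is wording only. All the data are already to be collected, and no planned analysis is lost. The one thing given up is the option of claiming a band result as evidence on variability.

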b) Initial Visit (at CHOA-Egleston)

Recruitment of the 20 to 40 pediatric subjects will take place at the Children's Healthcare of Atlanta at Egleston, when they are hospitalized with the diagnosis of new onset T1DM.

Enrolled participants will be interviewed in order to collect demographic information. The subjects will be randomized to either the FIXED group or the ICR group according to a computer-generated random sampling table. The subject and his/her caregivers will receive diabetes education while in the hospital in standard fashion. The subject and his/her caregivers will receive glucose monitoring education and training prior to hospital discharge. The subject and his/her caregivers will also receive a paper log to record the blood sugars, number of carbohydrates consumed, and insulin administered at each meal throughout the day.

Prior to discharge, all subjects will receive a regimen that includes a: 1) Meal-time insulin and carbohydrate regimen (# of units of insulin, # of carbohydrates, and/or ICR);

2) Evening dose of Glargine; 3) Hyperglycemia correction regimen for blood glucose levels > 199 mg/dL; and 4) Hypoglycemia treatment regimen for blood glucose levels < 70 mg/dL and/or symptomatic.

c) After Hospital Discharge and Between Clinic Visits

As per standard diabetes care, caregivers will report all blood glucose levels every day (to the study investigators) until the subject's initial clinic visit 4-6 weeks after diagnosis. All insulin adjustments will be made by the study investigators.

After the subject's first clinic visit, caregivers will contact the study investigators once a week to report blood glucose levels and the investigators will make adjustments as needed.

d) Diabetes Clinic Visits

All the diabetes clinic visits will occur at the Center for Advanced Pediatrics (CAP), approximately three miles from CHOA-Egleston Hospital. Subjects will attend clinic with one or more of the investigators approximately 1 and 4 months after enrollment.

At each clinic visit, subjects and their caregivers will answer standard diabetes questions, undergo a physical examination, and objective data (vital signs, glucose meter (GM) data, insulin dosing, and carbohydrate intake) will be collected by the study personnel.

B. STUDY POPULATION

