The plan is to enroll from 20 to 40 children and adolescent subjects with newly-diagnosed T1DM. Twenty will be randomized to the FIXED group and twenty will be randomized to the ICR group. The subjects will be selected from children and adolescents admitted to CHOA-Egleston with a diagnosis of new-onset Diabetes Mellitus. Participation in this study will be determined by a set of inclusion/exclusion criteria.

1) Inclusion Criteria

For enrollment in the study, subjects must: (1) Have Confirmed diagnosis of T1DM based on the most recent ADA criteria [16]; (2) Be 8 - 14 years of age; (3) Begin monitoring with a glucose monitor prior to discharge from the hospital; and (4) Have the ability to understand and be willing to adhere to the study protocol. (5) English or Spanish speakers.

2) Exclusion criteria

For enrollment in the study, subjects may not: (1) Have a clinically significant major organ system disease (i.e., hypertension, hyperlipidemia, or obesity); (2) Be on glucocorticoid therapy; (3) Have Type 2 Diabetes Mellitus; (4) Have Polycystic Ovarian Syndrome (PCOS); (5) Have a BMI > 85th %ile; (6) Have Acanthosis Nigricans; (7) Have any form of renal impairment; (8) Have Cystic Fibrosis; (9) Have Glucocorticoid-, Chemotherapeutic-, or any other Medication-induced form of Diabetes; (10) Be using any basal insulin other than Glargine insulin; (11) Have cognitive impairment (> 2 grades behind age-appropriate grade in school); (12) Be in Foster Care; (13) Have any history of DFCS involvement; and (14) If female, be pregnant or breast-feeding.

C. DATA MANAGEMENT

All data, including patient demographics, history, and laboratory tests will be collected on standardized forms and entered into an electronic database, REDCap. REDCap is a HIPPA-compliant, web-based, data capturing tool used in over 130 countries. Features include user-specific credentials, data-logging, longitudinal data modeling and more. Enrolled patients will be assigned a study ID. Subjects will only be identified in REDCap by their study ID. The patient's name, MRN and study ID will be kept in a secure file in a double lock in a filing cabinet under [name] supervision in the Emory Children's Center. Records will be maintained for 10 years as required for IRB studies.

D. OUTCOME MEASURES

1) Primary Outcome Measures

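### Blocks of 2 and 4, printed in the protocol of an unblinded single-hospital trial, make about one allocation in ten certain in advance to anyone who tracks the sequence

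*Combined protocol and SAP*

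**What the plan says.** Section 5.E (Randomization) gives the method: "Randomization will be performed by study statistician using random-permuted blocks of size 2 and 4". It adds "Randomization assignments will be placed in sealed, opaque envelopes to be stored" and "Study investigators will not be blinded to treatment assignment". It does not say whether the order of block sizes is random, whether the envelopes are numbered, or who holds and opens them. No stratification is described.

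Section 5.A.3(b) places all recruitment at one hospital: "Recruitment of the 20 to 40 pediatric subjects will take place at the Children's Healthcare of Atlanta at Egleston". Under 5.A.3(a), "The subjects will be contacted by the research study team while in the hospital during his or her initial diagnosis", and the same team confirms eligibility and obtains consent. Under 5.A.3(c), "All insulin adjustments will be made by the study investigators", so the investigators learn each participant's regimen. Section 5.B sets the size: "The plan is to enroll from 20 to 40 children and adolescent subjects with newly-diagnosed T1DM". One inclusion criterion in 5.B.1 is a judgement about whether the subject can follow, and will comply with, the protocol. Section 5.F records that the team expects the FIXED arm to do better because it asks for fewer calculations.

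**The concern.** Opaque envelopes hide the next card. They do not hide what the earlier cards imply once the block sizes are known. Every block of 2 or 4 ends in balance, so a running difference of two between the arms can arise only halfway through a block of 4. The next two allocations must then both go to the other arm. In an open-label trial with one apparent sequence, anyone who keeps count can see this.

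The stake is selective entry. A recruiter who expects one arm next could, without intending it, approach a family or not, or read the one judgement criterion more or less strictly. The trait most likely to be matched to an expected arm is perceived ability to manage carbohydrate counting, which could plausibly relate to glucose readings and caregiver stress. Section 5.E plans between-group tests and says effect sizes will feed later power calculations, so a distortion here could carry into the next trial.

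**Working it through.** The plan states no figure on predictability, so there is none to reproduce.

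**Inputs.** Block sizes 2 and 4, unblinded investigators (5.E); one hospital and 20 to 40 participants (5.A.3(b), 5.B); 1:1 allocation (5.B). Assumptions: a single sequence, the two sizes drawn at random with probability ½ each, and an observer who knows the sizes and all earlier allocations.

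**Step 1: certain allocations, long run.** A block is of size 4 with probability ½. It opens with two of the same arm (AABB or BBAA) in 2 of its 6 orderings, probability 1/3. Two allocations are then certain. Mean block length is (2 + 4)/2 = 3. The share is ½ × 1/3 × 2 / 3 = 1/9 = 11.1%. No other allocation is certain: at balance the arms are equally likely, and at a first difference of one the observer cannot tell a block of 2 from a block of 4.

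**Step 2: certain allocations at 20 and 40.** Let u(k) be the probability that a block starts after k allocations: u(0) = 1 and u(k) = ½u(k−2) + ½u(k−4), with u = 0 for negative k. For k = 0, 2, …, 16 this gives 1, 0.5, 0.75, 0.625, 0.6875, 0.6563, 0.6719, 0.6641, 0.6680, which sum to 6.22. Each start yields ½ × 1/3 × 2 = 1/3 certain allocations on average.
- 20 participants: 6.22/3 = 2.07, or 10.4%.
- 40 participants: the sum to k = 36 is 12.89, and 12.89/3 = 4.30, or 10.7%.

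A simulation of 4,000 sequences gave 2.03 and 4.30.

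**Step 3: guessing.** The observer always names the arm that is behind, and tosses a coin at balance.
- Block of 2: ½ + 1 = 1.5 correct.
- Block of 4 opening with a repeat (1/3): ½ + 0 + 1 + 1 = 2.5. Otherwise (2/3): ½ + 1 + ½ + 1 = 3. Mean 2.5/3 + 2 × 3/3 = 2.83.
- Long run: (½ × 1.5 + ½ × 2.83)/3 = 72.2%. Simulation gave 72% at both 20 and 40. Simple randomisation gives 50%.

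**Step 4: alternatives** (sizes equally likely and known to the observer; simulated).

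| Scheme | Certain, of 20 | Certain, of 40 | Best guess right | Mean final imbalance at 20 |
|---|---|---|---|---|
| 2 and 4, mixed | 2.0 | 4.3 | 72% | 0.22 |
| 4 and 6, mixed | 1.1 | 2.3 | 68–69% | 0.45 |
| 4, 6 and 8, mixed | 0.5 | 0.9 | 67–68% | 0.54 |
| all 4 | 6.7 | 13.3 | 71% | – |
| all 2 | 10 | 20 | 75% | – |

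The first imbalance figure can be checked by hand. At 20, the arms are uneven only if a block of 4 starts after allocation 18 (0.666 × ½ = 0.333) and opens with a repeat (1/3), which leaves a difference of 2: 0.333 × 1/3 × 2 = 0.22.

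**Step 5: what steering could do (illustration only).** Suppose every entry were shifted by d standard deviations on a prognostic trait, up or down according to the guessed arm. With guessing accuracy p, the spurious arm difference is about 2(2p − 1)d. At p = 0.72 this is 0.88d; at p = 0.67 it is 0.68d. For assumed d of 0.1 to 0.5, that is 0.09 to 0.44 SD, against 0.07 to 0.34 SD. Steering every entry is an extreme assumption, and the documents give no value for d.

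**The case against.** The plan already has the usual safeguards: two block sizes rather than one, opaque envelopes, and a list made by the statistician. Mixing the sizes brings certain allocations down from 33% (all 4) or 50% (all 2) to about 11%. Larger blocks lower guessing accuracy by only about five percentage points, because naming the lagging arm needs no knowledge of the sizes. This stands, and it limits what a change of block size can achieve.

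A reader might also infer more than the documents support:

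- *That the consent rate is biased.* Consent comes before randomisation, and Section 5.E treats it as a descriptive feasibility measure, not an arm comparison.
- *That families could be held back for the next slot.* Section 3 puts discharge at usually under 48 hours, consent is signed in hospital at first contact, and Section 5.E expects about 10 eligible patients a month, roughly one every three days. Not approaching a family, or judging it ineligible, is the more realistic route.
- *That the main stress test is undermined.* The scale is completed at enrolment, and the treatment-by-time interaction includes that baseline. A pure difference in starting level does not drive it, so the test is partly protected.
- *That recruiters know every earlier allocation.* This is an inference. The documents name a study team that recruits and investigators who adjust insulin. They do not say these are the same people, but they do not separate them.
- *That bias has occurred or is material.* Nothing shows this. The primary outcomes are feasibility summaries, and Section 5.E calls the secondary outcomes exploratory.

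**Conclusion.** The concern holds as a minor, cheaply reduced risk. About 10 to 11% of allocations are knowable with certainty and about 72% can be guessed, if the sizes are mixed at random with equal probability in one sequence and the observer knows the sizes and history. A single fixed size would be more predictable. The exposure is mainly in the glycemic variability comparison, the cross-sectional stress tests, the safety comparison and the effect sizes carried forward. The documents support a route to selection, not a finding of selection bias.

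**What to change.** Before further randomisation:

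1. Have the statistician generate a list without block size 2, using randomly varying permuted blocks of 4 and 6, or of 4, 6 and 8.
2. Replace the stated sizes in Section 5.E with a reference to a document that only the statistician holds.
3. State in Section 5.E who holds and opens the envelopes, that they are sequentially numbered, and that each is opened only after consent and eligibility are recorded.

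Step 1 makes the clearest difference to certain allocations: from about 10% to about 5.7% with 4 and 6, or 2.4% with 4, 6 and 8, even if the sizes became known. Step 2 takes away the knowledge on which certainty rests, though not the simple guess at the lagging arm. Step 3 stops entry being reconsidered once the card is seen; it does not stop prediction beforehand.

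The cost is a new list and a short amendment. Mean imbalance at 20 participants rises from about 0.2 to 0.45 (4 and 6) or 0.54 (4, 6 and 8). The largest possible imbalance at 20 is 4 with 4, 6 and 8; with 4 and 6 it stays at 2. The planned analysis is unaffected, and the change helps only participants not yet randomised.
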